Table 9: Analysis windows for immunogenicity, PD, PK, coagulation, serum sample for exploratory assessments (Illness visit schedule)	22
Table 10: Analysis windows for COVID-19 symptom assessment, SARS-CoV-2 RT-PCR sequencing NP swab, and vital signs (for Confirmed Illness visit schedule)	22

LIST OF ABBREVIATIONS

Abbreviation or Specialized Term	Definition
ADA	Anti-drug antibody
AE	Adverse event
AESI	Adverse events of special interest
ALP	Alkaline phosphatase
ALT	Alanine aminotransferase/transaminase
AST	Aspartate aminotransferase/transaminase
ATC	Anatomical therapeutic class
AUC	Area under the concentration-time curve
BLQ	Below the lower limit of quantification
BMI	Body mass index
C	Celsius
CI	Confidence interval
COVID-19	Coronavirus disease 2019
CTCAE	Common Terminology Criteria for Adverse Events
CSP	Clinical study protocol
CSR	Clinical study report
DBP	Diastolic blood pressure
ECG	Electrocardiogram
EOT	End of treatment
eCRF	Electronic case report form
FAS	Full analysis set
gCV	Geometric coefficient of variation
GMFR	Geometric mean fold rise
GMT	Geometric mean titer
gSD	Geometric standard deviation
ICF	Inform consent form
IV	Intravenously
IMP	Investigational medicinal product
IPD	Important protocol deviation
mAb	Monoclonal antibody
MedDRA	Medical Dictionary for Regulatory Activities
MRD	Minimum Required Dilution
nAb	Neutralizing antibody
NR	Not Reportable
NP	Nasopharyngeal
NQ	Not Quantifiable
NS	No Sample
LLOQ	Lower limit of quantification
PD	Pharmacodynamics
PK	Pharmacokinetics
RT-PCR	Reverse transcriptase polymerase chain reaction
SAE	Serious adverse event
SARS-CoV-2	Severe acute respiratory syndrome-coronavirus 2
SAP	Statistical Analysis Plan
SBP	Systolic blood pressure

Abbreviation or Specialized Term	Definition
SI	Standard International
SD	Standard deviation
SoA	Schedule of Assessments
TBL	Total bilirubin
TFLs	Tables, figures, and listings
ULN	Upper limit of normal
ULOQ	Upper limit of quantification
WHO	World Health Organization

AMENDMENT HISTORY

CATEGORY Change refers to:	Date	Description of change	In line with CSP?	Rationale
N/A	8/16/2022	Initial approved SAP	N/A	N/A
Other: Study design	20Nov2023	Study is early terminated. Participants remained in the study are to complete final assessments at least 6 months after their final dose of AZD7442. No additional dose of AZD7442 will be given.	Yes	On 30 March 2023, the FDA requested that the Sponsor halt further dosing for the ENDURE Study, given that AZD7442 (EVUSHELD) is not active against > 99% of the currently circulating SARS-CoV-2 variants in the USA, the benefit risk assessment may not be favorable. After consideration of the FDAs request, the Sponsor has decided to terminate this study.
Other: Changes to CSP planned analysis	20Nov2023	Additional section added to explain the analysis set definition.	N/A	Clarify the participant inclusion / exclusion and participant visit inclusion / exclusion differences in the analysis set definition.
Other: Timing of the analyses	20Nov2023	Remove interim analysis and only final analysis is planned for the study	Yes	Due to study design change, only final analysis is needed.
Other: NLF PK analysis set	20Nov2023	Addition of NLF PK analysis set	N/A	Clarify NLF PK concentration analysis set
Other: Visit Window	20Nov2023	Remove Day 1 pre-dose time point from the visit window for Serum and NLF PK parameters.	N/A	
Other: Protocol deviation category	20Nov2023	Align protocol deviation categories with PDMP	N/A	Protocol deviation monitoring plan (PDMP) is updated, this change is to align SAP with the PDMP.
Data presentations	20Nov2023	Remove Region from the subgroup presentation	N/A	Only participants in US is enrolled.
Other: Partial date imputation	20Nov2023	Addition of partial COVID-19 vaccination date imputation method	N/A	Method to impute incomplete date that was collected for statistical analysis.
Data presentations	20Nov2023	Concomitant medication summaries will use ATC level 4 instead of level 2	N/A	To display more specific drug category

Statistical analysis method	20Nov2023	Further clarify the correlation calculation method using mixed model for repeated measurements and bootstrapping.	N/A	Clarify the statistical method used for calculation of nAb and PK concentration correlation.
Data presentations	20Nov2023	Clarify 2 assays are used for nAb titers	N/A	Two assays: one for SARS-CoV-2 authentic virus and the other pseudovirus nAb are both collected.
Other: Record exclusion for analyses	20Nov2023	For serum / NLF PK and nAb analyses, clarify how the individual records will be excluded per protocol deviation occurrence	N/A	Clarify under each analysis set, due to protocol deviations that could impact the concentration and / or nAb titer values, certain data points need to be excluded from the analyses.
Other: NLF PK derivation and analysis methods	20Nov2023	Addition of NLF PK data definition, derivation and associated statistical analysis methods	N/A	Adding details on the analyses of NLF PK data
Other: COVID-19 variant analyses	20Nov2023	Addition of variant analyses	N/A	Adding details on the analyses of variants
Other: Censoring method for Symptomatic illness endpoint	20Nov2023	Addition of various censoring rules to encompass different scenarios	N/A	Further clarifying censoring method for counting incidence of illnesses.
Other: Add additional safety analyses	20Nov2023	Addition of Grade ≥ 3 event and embolic and thrombotic event definition and analyses	N/A	Additional safety analyses deemed necessary
Other: Lab test	20Nov2023	Adjust lab CTCAE table to align with protocol required lab tests	Yes	To align with CSP

1 INTRODUCTION

The purpose of this document is to give details for the statistical analysis of study D8850C00010 supporting the clinical study report. The reader is referred to the most recent versions of the Clinical Study Protocol (CSP) and the Case Report Form (CRF) for details of study conduct and data collection.

The term IMP (investigational medicinal product) is used throughout this SAP to refer to AZD7442, a combination product of two monoclonal antibodies (tixagevimab [AZD8895] + cilgavimab [AZD1061]). Approximately 200 participants who meet the eligibility criteria for the study will be randomized in a 1:1 ratio to one of 2 open-label AZD7442 treatment arms:

- Arm A: AZD7442 600 mg IM on Day 1 followed by 300 mg IM every 3 months (Q3M) for 12 months (a total of 5 doses)
- Arm B: AZD7442 1200 mg IV on Day 1 followed by 600 mg IM every 6 months (Q6M) for 12 months (a total of 3 doses)

1.1 Objectives and Endpoints

Table 1: Objectives and Endpoints

Objective	Endpoint
Primary	
To evaluate the safety and tolerability of AZD7442	AEs, SAEs, and AESIs
To evaluate the immunogenicity of AZD7442	Incidence of ADA in serum
Secondary	
To evaluate the PK of AZD7442 in serum	
 • Serum AZD7442 concentrations • PK parameters
To determine anti-SARS-CoV-2 nAb levels in serum after administration of AZD7442	Changes from baseline in GMTs and GMFRs values in SARS-CoV-2 nAbs (wild-type assay or pseudo neutralization assay)
Exploratory	
To estimate the efficacy of AZD7442 for the prevention of COVID-19	
 • Incidence of SARS-CoV-2 RT-PCR-positive symptomatic illness • Incidence of participants who have a post-treatment response (negative at baseline to positive at any time post-baseline) for SARS-CoV-2 nucleocapsid antibodies

To estimate the efficacy of AZD7442 for the prevention of severe or critical symptomatic COVID-19	Incidence of SARS-CoV-2 RT-PCR-positive severe or critical symptomatic illness and COVID-19 deaths
To evaluate the PK of AZD7442 in nasal fluid	Nasal AZD7442 concentrations
To quantify SARS-CoV-2 viral loads in infected participants treated with AZD7442 (Illness Visits)	Viral genome copies in NP swabs at Illness Visits as determined by RT-PCR
To characterize resistance to AZD7442 (Illness Visits)	Genotypic analysis and biochemical and/or susceptibility analysis of SARS-CoV-2 variants to AZD7442
To assess additional immune responses in participants treated with AZD7442 (Illness Visits)	Other exploratory assays for humoral, mucosal, and cellular immune responses may be performed based upon emerging safety, efficacy, and pharmacodynamic data

Abbreviations: ADA = Antidrug antibody; AE = Adverse event; AESI = Adverse event of special interest; COVID-19 = Coronavirus disease 2019; GMT = Geometric mean titers; GMFR = Geometric mean fold rise; nAb = Neutralizing antibody; NP = Nasopharyngeal; PK = Pharmacokinetic; RT-PCR = Reverse transcriptase polymerase chain reaction; SAE = serious adverse event; SARS-CoV-2 = Severe acute respiratory syndrome-coronavirus 2.

1.2 Study Design

This is a Phase II randomized, open-label, multicenter, dose-ranging study to assess the safety, immunogenicity, PK, and PD profiles of AZD7442 repeat dose regimens. The study will enroll adults and pediatric individuals (≥ 12 years of age weighing at least 40 kg) who are moderate to severely immunocompromised due to an underlying disease or are taking immunosuppressive medications and therefore unable to mount an adequate immune response to COVID-19 vaccine.

Approximately 200 adults and pediatric individuals, who meet the eligibility criteria, will be randomized in a 1:1 ratio to one of 2 AZD7442 treatment arms:

- Arm A (100 participants): AZD7442 600 mg administered intramuscularly (IM) on Day 1 followed by 300 mg IM Q3M for 12 months (a total of 5 doses)
- Arm B (100 participants): AZD7442 1200 mg administered intravenously (IV) on Day 1 followed by 600 mg IM Q6M for 12 months (a total of 3 doses)

An End of Treatment (EoT) Visit will be conducted at 15 months in both arms (3 months after the final dose of AZD7442). After the EoT Visit, the participant will enter the follow-up period. Participants will be followed for safety for an additional 9 months after the EoT Visit, i.e., through 12 months after the participant's final dose of AZD442.

Participants who discontinue IMP administration due to premature termination of the study

will remain in the study to complete visits/assessments (except those related to monitoring of IMP administration; see CSP Section 1.3) for at least 6 months after their final dose of AZD7442.

1.3 Sample Size

Approximately 200 participants will be randomized to study intervention: 100 participants to Arm A (AZD7442 600 mg IM on Day 1 then 300 mg IM Q3M for 12 months) and 100 participants to Arm B (AZD7442 1200 mg IV on Day 1 then 600 mg IM Q6M for 12 months).

If the true AE rate is 3%, the probability of observing at least one AE in 100 participants is 95%. The number of participants in the study would also allow for assessment of immunogenicity based on ADA prevalence observed in PROVENT (D8850C00002; NCT04625725).

2 CHANGES TO PROTOCOL PLANNED ANALYSES

The CSP details record level exclusions for the nAb evaluable analysis set, following the point at which they receive an alternative COVID-19 monoclonal antibody (mAb). The purpose of an analysis set should be to exclude at the participant level. Therefore, this additional detail has been removed from the analysis set definition in Section 3.2, and record level exclusions for nAb are detailed in Section 4.2.2.4.2. These include exclusions following receipt of an alternative COVID-19 mAb by excluding nAb samples from the date a participant had a protocol deviation recorded for receiving a restricted medication, as detailed in CSP Section 6.5. Although such medications are allowed for treatment of COVID-19 or during the follow-up period (starting ≥ 3 months after the last dose of IMP), nAb samples are also excluded following the date of a positive SARS-CoV-2 RT-PCR (defined in Section 4.2.3.4.1), and nAb samples collected during illness visits are to be summarized separately to main study visits in the planned analyses. Hence this record level exclusion is in line with what was detailed in CSP.

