	Participants may take concomitant medications prescribed by their primary care provider for management of chronic medical conditions and/or for health maintenance. Primary care providers or, where appropriate, Investigators should prescribe appropriate concomitant medications or treatments deemed necessary to provide full supportive care and comfort during the study. Participants who develop COVID-19 after receiving IMP should be treated according to local standard of care, including investigational agents outside a clinical trial setting.	
	
 Contraceptive methods 	
 Allowed, with guidance from health care professional taking into consideration any risks and benefits.
Restricted	
 Investigational or authorized under early access or EUA products indicated for the treatment or prevention of SARS-CoV-2 or COVID19) Convalescent COVID-19 plasma and sera 	
 Note: For participants who develop COVID-19, receipt of approved/licensed products options are permitted, and they should be treated according to local standard of care, including investigational agents under EUA or equivalent regulations. Receipt of approved/licensed treatments for the prevention of COVID-19 are permitted during the follow-up period (starting \geq 3 months after last dose of AZD7442) as per local guidelines/standard of care and should be documented as concomitant medication.

COVID-19, coronavirus disease 2019; EUA, Emergency Use Authorization; HIV, Human immunodeficiency virus; IMP, investigational medicinal product; IVIG, intravenous immunoglobulin; SARS-CoV-2, severe acute respiratory syndrome-coronavirus-2.

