9.3 Populations for Analyses

The following populations are defined in [Table 10](#).

Table 10 Populations for Analysis

Population/Analysis set	Description
Enrolled	All participants who sign the ICF.
Full analysis set	All randomized participants who receive at least one dose of IMP. Participants will be assigned according to their randomized treatment according to the intent-to-treat principle.
Safety analysis set	All participants who have received at least one dose of IMP. Participants will be assigned in this analysis set by the arm of treatment they actually received.
PK analysis set	All participants in the safety analysis set who received AZD7442 and who had at least one quantifiable serum PK observation post dose will be included in the PK analysis dataset.
ADA evaluable analysis set	All participants in the safety analysis set who have a non-missing baseline AZD7442 ADA result and at least one non-missing post-baseline AZD7442 ADA result.
nAb evaluable analysis set	All participants in the safety analysis set from whom blood samples are assumed not to be affected by factors such as protocol violations, and who had at least one quantifiable serum observation post dose. At any time during the study, participants will be excluded from this analysis set at the point at which they receive an alternative COVID-19 mAb.

ADA, antidrug antibody; COVID-19, coronavirus disease 2019; ICF, informed consent form; IMP, investigational medicinal product; nAb, neutralizing antibody; PK, pharmacokinetic.

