4.2.2.4.2 SARS-CoV-2 Neutralizing Antibodies

SARS-CoV-2 nAb analysis will be based on actual treatment in nAb Evaluable Analysis Set. Two (2) assays will be used to provide titers for authentic virus and pseudovirus nAb.

If a participant has any protocol deviation which is identified as a record-level exclusion for the immunogenicity analysis in Table 5 of the most recent version of the PDMP, then their SARS-CoV-2 nAb samples collected after the date of deviation will be excluded from the analyses.

Due to the change in dosing schedules between CSP V3.0 (dated 09 December 2022) and CSP V4.0 (dated 06 June 2023), there may be visits with a mixture of participants who received and participants who did not receive IMP in previous visit. Therefore, any SARS-CoV-2 nAb samples from participants who did not receive IMP according to the SoA of CSP V3.0, irrespective of the visit date being before or after the effective date of CSP V4.0, will be excluded from analyses at all subsequent visits.

SARS-CoV-2 nAb assessments scheduled for collection pre-dose, but instead collected post-dose at a visit where dosing is done, will be excluded from the analyses.

For participants who receive a COVID-19 vaccine after the first dose of IMP, data collected after receipt of the vaccine will also be excluded. Furthermore, for participant who receive a positive SARS-CoV-2 RT-PCR (defined in Section 4.2.3.4.1), data collected after infection will also be excluded, except in the case that SARS-CoV-2 nAb samples were collected during an illness visit.

Descriptive statistics for titer and fold rise will include number of participants, geometric mean, geometric standard deviation (gSD), 95% confidence interval (CI), minimum and maximum. This will be reported separately for nAbs collected during treatment period and illness visits (the illness visits where the series corresponds to positive RT-PCR test, as defined in Section 4.2.3.4.1, will be used in the summary).

A scatter plot of log₂ transformed titers with log₂ transformed serum concentration for each treatment arm, along with the bias-adjusted bootstrapped correlation coefficient, 95% CI and convergence (%) (see Section 4.2.2.2.1).

Summaries will also be split by the previous COVID-19 vaccination status (as defined in Section 4.1.5.1). Samples from 2 separate assays will be analysed using the same methods as described here.

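### The SAP says its neutralizing antibody record exclusion matches the protocol, but it is triggered by recorded deviations and so has no stated rule for an alternative COVID-19 antibody that the protocol permits

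*SAP*

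**What the plan says.** Protocol 9.3 (Table 10) sets a receipt rule for the nAb evaluable set. At any time in the study, "participants will be excluded from this analysis set at the point at which they receive an alternative COVID-19 mAb". Whether the use was allowed makes no difference. Appendix G (Version 2.0) gives the reason: to stop other antibodies affecting the nAb measurements.

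Protocol 6.5 (Table 7) leaves two permitted routes to such a product. For participants who develop COVID-19, "they should be treated according to local standard of care, including investigational agents under EUA or equivalent regulations". For prevention: "Receipt of approved/licensed treatments for the prevention of COVID-19 are permitted during the follow-up period", with a parenthesis that dates this from 3 months or more after the last dose.

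SAP Section 2 takes the receipt rule out of the analysis-set definition and replaces it with a record-level rule, "excluding nAb samples from the date a participant had a protocol deviation recorded for receiving a restricted medication". It acknowledges both permitted routes and offers two safeguards: nAb samples after a positive RT-PCR are also dropped, and illness-visit samples are summarized separately. It concludes: "Hence this record level exclusion is in line with what was detailed in CSP".

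The operative text is SAP 4.2.2.4.2. If a deviation is listed as a record-level exclusion in Table 5 of the protocol deviation management plan (PDMP), "then their SARS-CoV-2 nAb samples collected after the date of deviation will be excluded from the analyses". The section also removes samples after a COVID-19 vaccine, after a missed dose, when mistimed relative to dosing, and after infection, "except in the case that SARS-CoV-2 nAb samples were collected during an illness visit". It does not name receipt of an alternative mAb as a trigger.

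**The concern.** The protocol's trigger is a pharmacological fact: another antibody is in the serum. The SAP's trigger is a compliance fact: someone logged a deviation. The two coincide only when every alternative mAb is prohibited, and Table 7 says that is not so. Both SAP safeguards concern infected participants, so neither reaches an uninfected participant who takes a licensed preventive mAb within the rules.

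A titer raised by another product would then count as a response to AZD7442 in the geometric mean titer (GMT) and the geometric mean fold rise (GMFR), both secondary endpoints. It would also enter the titer-concentration correlation of SAP 4.2.2.2.2, paired with an AZD7442 concentration that does not explain it. Because Section 2 presents the rule as equivalent to the protocol, a reader of the report would not know to look for this.

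**Working it through.** The plan gives no figure on this point. The check is a comparison of rules, then a count of exposed samples, then an illustration of size.

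**1. The two rules side by side**

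| Situation | Protocol 9.3 | SAP 2 and 4.2.2.4.2 |
|---|---|---|
| mAb use logged as a restricted-medication deviation (including preventive use of a product available only under EUA) | Excluded from receipt | Excluded, provided PDMP Table 5 lists it |
| Therapeutic mAb, RT-PCR positive, main visit | Excluded | Excluded by the RT-PCR rule |
| Therapeutic mAb, RT-PCR positive, illness visit | Excluded | Kept, summarized separately |
| Therapeutic mAb, but the case is not RT-PCR positive under SAP 4.2.3.4.1 (no result, or central negative over local positive) | Excluded | No stated trigger |
| Permitted licensed preventive mAb, uninfected, main visit | Excluded | No stated trigger |

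The last row breaks the equivalence claim.

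**2. Which main-visit samples are exposed**

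Inputs:
- Dosing and nAb sampling days from protocol Tables 1 and 2.
- The Early Discontinuation nAb sample from protocol Table 3.
- The early-termination visit rules in protocol 1.3.
- The SAP missed-dose rule, read as removing visits after the one where the dose was missed. Dose-day samples are taken predose, which supports this reading.

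*Reading A: the permitted window runs from 3 months (about 91 days) after the last dose.* Samples at least 91 days after the last dose that survive the missed-dose rule are:
- Arm B, last dose Day 183: Day 274 (274 − 183 = 91 days) and Day 365 or the Early Discontinuation visit in its place (365 − 183 = 182 days). The latter falls in the SAP window of Days 320-410.
- Arm B, last dose Day 1: Day 92 (91 days) and Day 183 (182 days).
- Arm A, last dose Day 1, 92, 183 or 274: only the sample at the next dosing visit, 91 days later. The Early Discontinuation sample at 182 days follows a missed dose and is removed.
- Either arm, last dose Day 365: Day 456 (91 days), plus any later Early Discontinuation sample.

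Samples at 91 days sit on the boundary of the permitted window, so little or no permitted use can precede them. The 182-day Arm B sample is the main exposure.

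*Reading B: the follow-up period is Days 457-729, as headed in protocol Table 3.* The scheduled visits at Months 18, 21 and 24 collect no nAb sample. Only an Early Discontinuation sample after Day 456 is left. It maps to the open-ended Day 456 window, where SAP 3.3.2 keeps the result closest to Day 456, so it counts only if no nearer sample exists.

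**3. Size, by assumption**

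The log2 GMT is the mean of the log2 titers. If a share f of the titers at a visit is raised k-fold, that mean rises by f × log2(k), so the GMT is multiplied by k^f. The GMFR changes by the same factor, because predose titers are unaffected.

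| | f = 1% | f = 5% | f = 10% |
|---|---|---|---|
| k = 4 | 4^0.01 = 1.01 | 4^0.05 = 1.07 | 4^0.10 = 1.15 |
| k = 16 | 16^0.01 = 1.03 | 16^0.05 = 1.15 | 16^0.10 = 1.32 |

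With the planned 100 per arm all contributing, f = 1% is one participant and f = 10% is ten. The documents give neither f nor k. At k = 100 the factors would be 1.05 for f = 1% and 1.58 for f = 10%.

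**The case against.** The best defence is that the gap is narrow and its effect minor. Much of that stands.

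- A reader might infer that permitted preventive use definitely opens at about Day 274 in Arm B and leaves 91 days exposed. That holds only under Reading A. Under Reading B, preventive use between Day 274 and Day 365 falls inside the treatment period, would be a deviation, and would come under the SAP's own rule. The parenthesis in Table 7 and the heading of Table 3 pull in different directions, and the documents do not settle it.
- A reader might infer a general bias between arms. Reading A does expose Arm B more, but chiefly through one sample in participants last dosed on Day 183. Participants last dosed on Day 365 stand alike in both arms, and the numbers in each group are not given.
- A reader might take the SAP as removing nothing except after a deviation or a positive RT-PCR. In fact 4.2.2.4.2 also acts on vaccination, missed doses and mistimed samples, and PDMP Table 5 may hold further triggers.
- A reader might infer that illness-visit titers inflate the main GMT. They cannot: they are reported separately, the SAP says so, and they are left out of the correlation. Infection already confounds them.
- The endpoint is secondary and descriptive, no hypothesis is tested, and nothing shows that any participant took a licensed preventive mAb.

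None of this repairs the equivalence sentence. The SAP names the permitted preventive route and then argues only from infection and illness visits. It already uses a receipt trigger for COVID-19 vaccines, which are also permitted outside 14 days either side of a dose.

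**Conclusion.** The concern holds as a narrow but real mismatch. Protocol 9.3 excludes on receipt of any alternative COVID-19 mAb. The SAP's mAb-related exclusion depends on a recorded deviation, and no stated rule covers permitted preventive use in an uninfected participant. The claim that nothing has changed from the protocol is therefore wrong as written, subject to PDMP Table 5, which could not be checked.

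The exposed samples are few under Reading A and close to none under Reading B. The GMT factor of about 1.01 to 1.32 illustrates assumed f (1% to 10%) and k (4 to 16). It is not an estimate for this trial, and the documents do not support stating that the GMT is inflated by any given amount. The correction is worth making because it is cheap and restores the rule that the protocol set.

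**What to change.** 1. In SAP 4.2.2.4.2, exclude main-visit nAb samples, and so their titer-concentration pairs, from the recorded concomitant-medication date of any non-study COVID-19 mAb, whether or not a deviation was logged. This mirrors the existing vaccine rule.
2. For illness-visit titers, either apply the same rule or declare their retention after a therapeutic mAb as a change from the protocol.
3. Correct the equivalence sentence in SAP Section 2. If the deviation rule is kept, list it as a change from the protocol.
4. Reconcile two wordings: Section 2 excludes from the date of the deviation, while 4.2.2.4.2 excludes after it. The sponsor should also reconcile the follow-up period in protocol Table 7 with that in Table 3, since it decides which uses count as deviations.

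Extending the rule to convalescent plasma is optional and goes beyond the protocol's wording.

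The cost is a few lines of SAP text, a medication-code lookup on dates that protocol 6.5 already requires, and the loss of a few samples.
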